#### **5.6.4 Laboratory Data**

Laboratory data will be summarized by treatment group for each assessment visit using descriptive statistics of absolute values and change from baseline values. In addition, the frequency of participants with abnormal laboratory values will be summarized by treatment group.

#### **5.6.5 Vital Signs**

Vital signs assessments include systolic blood pressure, diastolic blood pressure, and pulse rate measured throughout the study. Vital sign measurements will be summarized by treatment group for each assessment visit using descriptive statistics of absolute values and change from baseline values. In addition, the frequency of participants with abnormal results will be summarized by treatment group.

#### **5.6.6 ECGs**

ECG data will be summarized by treatment group for each assessment visit using descriptive statistics of absolute values and change from baseline values for the following parameters:

- Heart rate
- QRS duration
- RR interval
- PR interval
- QT intervals (including QTcF)

For QTcF, the summary will also include 2-sided 90% confidence interval at each time-point.

In addition, ECG overall interpretations will be summarized by treatment group and visit.

#### **5.6.7 Columbia-Suicide Severity Rating Scale (C-SSRS)**

The **C-SSRS** is an assessment tool used to assess the lifetime suicidality of a participant (C-SSRS at baseline) as well as any new instances of suicidality (C-SSRS since last visit). The structured interview prompts recollection of suicidal ideation, including the intensity of the ideation, behavior, and attempts with actual or potential lethality.

Suicidal ideation, suicidal behavior, and self-injurious behavior without suicidal intent will be summarized by treatment group. In addition, change from baseline to worst post-baseline assessment in suicidality categories will be summarized by treatment group.

## **5.7 OTHER ANALYSES**

### **5.7.1 Summaries of Conduct of Study**

The summary of study conduct will include a description of the following items by treatment arm:

- Number of participants enrolled and randomized
- Number of participants included in each analysis set
- Number and percentage of participants who prematurely withdrew from the study or from study treatment (including the reasons for discontinuation and the distribution of these discontinuations by time-windowed visit)
- Incidence of protocol deviations – overall and by four main categories (inclusion criteria, exclusion criteria, medication and procedural)
- Stratification factor reported in IxRS and used for randomization
- Number of participants with home nursing
- Number of participants initiating or changing symptomatic treatment of AD during the study

Major protocol deviations and premature withdrawals will be listed.

### **5.7.2 Summaries of Treatment Group Comparability**

Demographics and baseline characteristics (including age, sex, medical history, randomization stratification factors) will be summarized descriptively by treatment arm as assigned for the ITT analysis set using:

- means, SDs, medians, and ranges for continuous variables
- counts and proportions for categorical variables

Exposure to AD concomitant medication (including post-baseline initiation or change in dose) will be summarized by treatment arm for the ITT analysis set.

### **5.7.3 Immunogenicity Analyses**

Immunogenicity analyses include the evaluation for antibodies against gantenerumab, including the determination of antibody titers. The results of the confirmatory assay will be presented as a frequency table summarizing baseline and post-baseline results.

A listing of participants with positive ADA status per confirmatory assay and titer result will be provided.

#### **5.7.4 Summaries of COVID-19 Impact on the Trials**

Studies GRADUATE I and GRADUATE II were ongoing during the COVID-19 pandemic. Consequently, to monitor the potential impact of the pandemic on the trials, we will provide a specific set of descriptive analyses related to COVID-19 by treatment arm for the ITT analysis set (see [Table 2](#)), including:

- Demographic and Baseline Characteristics in Participants with Confirmed/Suspected COVID-19
- COVID-19 AEs (see Section [5.6.2](#))
- COVID-19 related Protocol Deviations
- Missed doses due to COVID-19
- Study discontinuations due to COVID-19 as determined by the adjudication committee for ICEs
- Study drug administrations of 1020 mg Q4W
- Remote scale administrations
- Duration of study site closure

#### **5.7.5 Amyloid PET Substudy**

The objective of the GRADUATE I and GRADUATE II longitudinal amyloid PET substudies is to assess changes in brain amyloid load over time using the change in florbetaben or flutemetamol from baseline to the last amyloid PET visit in the Standard Uptake Value Ratio (SUVR).

Two amyloid PET ligands are allowed in the GRADUATE I and GRADUATE II longitudinal amyloid PET substudies to provide assessment of  $\beta$ -amyloid protein deposition according to country and site availability: radiopharmaceuticals florbetaben-F18 and flutemetamol-F18. However, the same ligand has to be used for the same participant throughout the study (e.g., if a participant has been enrolled in the main study with a positive florbetaben PET scan, only florbetaben will be allowed and used for the longitudinal follow-up scans for the participant).

Centiloid mapping will be completed for SUVR data from the two amyloid PET ligands. The primary amyloid PET outcome measure is the change in amyloid PET Centiloid from baseline to Week 116.

##### **5.7.5.1 General considerations on Amyloid PET statistical analyses**

With the Centiloid endpoint, data from both tracers will be pooled and analyzed together. Separate analysis by tracer with the Centiloid endpoint may also be conducted as appropriate. When SUVR metrics is the endpoint, the analysis will be done separately and reported separately for each tracer, when possible.

Missing values will not be imputed.

The amyloid PET analyses will be performed on the Amyloid-PET-mITT analysis set (see [Table 2](#)), unless otherwise specified, and participants will be analyzed according to the treatment assigned at randomization by IxRS.

### 5.7.5.2 Summaries of Treatment Group Comparability

Demographics and baseline characteristics (including age, sex, medical history, randomization stratification factors) will be summarized descriptively by treatment arm as assigned for both the Amyloid-PET-mITT analysis set and the Amyloid-PET-longitudinal analysis set (see [Table 2](#)) using:

- means, SDs, medians, and ranges for continuous variables
- counts and proportions for categorical variables

### 5.7.5.3 Visit Windowing

For amyloid PET assessments, due to the long time between scheduled assessments, time windows based on study days, as defined in [Table 7](#), will be used. Study days are defined based on days on study since the date of the first dose, with the day of the first dose being study day 1.

**Table 7 Time Windows for Amyloid PET Assessments**

Visit	Target day	Time window
Baseline	1	Up to day 35
Week 52	365	281, 449
Week 116	813	645, 897

For Week 116, the time window will cover the week 104 timepoint as well. In case of more than one assessment within a time window, the assessment with the date closest to the target day is selected. For the combined window of Week 104 and 116, the target day is the Week 116 assessment day.

Because of visit windowing, data collected at an early termination visit will be summarized at the corresponding visit as defined by the time window. For participants who have discontinued treatment early, if a PET scan is performed more than 56 days (early termination visit expected 14 days after last dose, followed by time window per protocol for early termination is  $\pm 42$  days) after the date of last dose, the PET scan will not be used for the analysis.

The end of a substudy is defined as the date when all participants enrolled in the substudy have:

1. completed the last required amyloid PET scan (Week 116), or
2. completed an early termination scan, or
3. discontinued from the main study.

#### 5.7.5.4 Definition of the Estimand for Amyloid PET

The scientific question of interest for the amyloid PET substudies is to assess the effect of the intended study treatment on the PD endpoint, change from baseline in amyloid load burden at Week 116, in the absence of a substantial impact of the COVID-19 pandemic and as if treatment discontinuation would not have occurred.

The primary Amyloid PET estimand is thus described by the following attributes:

- **Target Population:**  
Early (prodromal to mild) AD population as identified by the inclusion and exclusion criteria, see Sections 4.1.1 and 4.1.2 of the substudy protocols and Sections 4.1.1 and 4.1.2 of the main study protocols
- **Variable:**  
Change from baseline to Week 116 in amyloid PET Centiloid
- **Treatment:**  
Prescribed study drug including up-titration to the target dose
- **Population-level summary:**  
Difference in variable means between treatment arms
- Intercurrent events
  - Substantial reduction in drug exposure due to the COVID-19 pandemic (defined as  $\geq 4$  missed dose-months)
  - Treatment discontinuation due to any reason

Amyloid PET is listed in the protocol under “Pharmacodynamic Biomarker Objective”. Considering that Amyloid PET primarily aims at estimating the Pharmacodynamic effect of the drug, rather than a direct measure of clinical efficacy, reporting treatment effect estimated “as if there were no treatment discontinuations and no substantial reduction in exposure due to COVID-19 pandemic” (thus using a hypothetical strategy) addresses the scientific question of interest.

#### Details for Definition of Variable

The Centiloid variable will be used rather than the original SUVR, because it allows to combine data from different tracers, by mapping SUVR values to a standardized scale. The Centiloid variable is the current common standard in the scientific community.

The primary SUVR measure of interest is computed using a weighted composite target region and whole cerebellum as reference region. The weighted composite target region is composed of (both left and right side):

- frontal lobe,
- parietal lobe,
- temporal lobe lateral,

- cingulum posterior and
- anterior cingulate gyrus

Each region is weighted by its own volume. The Centiloid conversion is a linear transformation of SUVR with tracer-specific parameters that are given below:

**Centiloid Equation:**

$$CL = \text{SlopeCL} \times \text{SUVR} + \text{InterceptCL}$$

CL= Centiloids; SlopeCL= slope; SUVR= standard uptake value ratio of the target region; InterceptCL= intercept.

The pertinent values for the two tracers are:

**Table 8 Primary Centiloid Equation Parameters**

Tracer	Reference	Slope	Intercept
Florbetaben-F18	whole cerebellum	175.6	-174.2
Flutemetamol-F18	whole cerebellum	143.5	-141.1

**5.7.5.5 Main Analytical Approach**

An MMRM will be used to estimate the mean change in Centiloid from baseline to Week 116 within each of the substudies. The model will include the change from baseline in Centiloids as the dependent variable, while adjusting for treatment arm (as categorical), visit (as categorical), APOE ε4 status (as categorical; carrier vs non-carrier), type of tracer (as categorical; Florbetaben vs Flutemetamol), baseline Centiloid, baseline Centiloid-by-visit and treatment-by-visit interaction. Visit will be treated as the repeated variable within a participant. An unstructured variance-covariance matrix will be applied to model the within-participant errors; in the case of non-convergence, compound symmetry will be used, together with a robust estimator of standard error (“sandwich” estimator).

In line with the estimand definition, data acquired after the ICE “Substantial reduction in drug exposure due to the COVID-19 pandemic” (as defined in [Table 3](#)) or more than 56 days from treatment discontinuation will be excluded from the analysis and treated as missing for the primary analysis purposes.

There will be no data imputation for missing data. However, the MMRM provides unbiased estimates and valid inference in the presence of missing data, under the MAR (missing at random) assumption.

The difference in least squares means between active drug and placebo arms at Week 116 will be estimated and presented alongside p-value and the 95% confidence interval for treatment difference. A p-value <0.0001 will be regarded as a statistically significant evidence, irrespective of the results of the other primary/secondary endpoints

(along the lines of the [Haybittle–Peto](#) rule, and thus maintaining the overall type-I error within the study).

### **5.7.5.6 Supplementary analyses**

Changes in weighted Composite Summary region SUVR (for each tracer) and Centiloids from baseline will be summarized using descriptive statistics.

Based on the same model as specified in the Section [5.7.5.4](#), the change from baseline to Week 52 in Centiloids will also be reported as supplementary analysis.

Additionally, the number and proportion of participants with values below or equal to the positivity threshold will be summarized for each assessment time point. Centiloid zero is the mean amyloid burden for a typical population of young healthy controls, and 100 Centiloid is the typical mean of a population with AD. The Centiloid value of 24 is consistent with the diagnostic amyloid positivity threshold ([Klunk et al. 2015](#); [Navitsky et al. 2018](#)) (see Section [5.7.5.3](#) for definition of Centiloid **Error! Reference source not found.**).

A chi-square test (or Fisher’s exact test, whichever is appropriate) will be used to compare the proportions of participants with values below or up to the positivity threshold between the active drug and placebo arm.

In order to account for the potential impact of missing values, a completers analysis will be performed, i.e., restricting the analysis to participants who completed the visit with non-missing data.

### **5.7.6 Tau PET Substudy**

There is a single tau PET substudy enrolling subjects from both studies (WN29922/WN39658 Longitudinal Tau PET Substudy). This substudy utilizes [F]GTP1 (RO6880276) as tau PET radioligand.

Statistical analyses will be conducted on tau PET Median Standardized Uptake Value Ratios (SUVR) in the following four target regions of interest. In composite target regions, each region is weighted by its own volume.

- A temporal composite target region. This region is composed of (both left and right):
  - anterior and posterior superior temporal gyrus,
  - posterior temporal lobe,
  - fusiform gyrus,
  - middle and inferior temporal gyrus;

- A medial temporal composite region not including the hippocampus, composed of (both left and right):
  - Amygdala,
  - Parahippocampus,
  - Anterior medial and lateral temporal lobe;
- Frontal lobe (both left and right);
- Parietal lobe (both left and right);

The inferior cerebellar grey matter will be used as reference region for the calculation of median SUVRs for all four target regions considered.

All the statistical analyses will be based on the Tau-PET-mITT analysis set (see [Table 2](#)) unless otherwise specified.

### 5.7.6.1 Summaries of Treatment Group Comparability

Demographics and baseline characteristics (including age, sex, medical history, randomization stratification factors) will be summarized descriptively by treatment arm as assigned for both the Tau-PET-mITT analysis set and the Tau-PET-longitudinal analysis set (see [Table 2](#)) using:

- means, SDs, medians, and ranges for continuous variables
- counts and proportions for categorical variables

### 5.7.6.2 Definition of the Estimand

The scientific question of interest for the Tau PET substudy is to assess the effect of the intended study treatment on the PD endpoint, change from baseline in tau PET median SUVR at Week 116, in the absence of a substantial impact of the COVID-19 pandemic and as if treatment discontinuation would not have occurred. The same estimand will be considered for all four median SUVRs regions.

The primary Tau PET estimand is thus described by the following attributes:

- **Target Population:**  
Early (prodromal to mild) AD population as identified by the inclusion and exclusion criteria, see Sections 4.1.1 and 4.1.2 of the substudy protocols and Sections 4.1.1 and 4.1.2 of the main study protocols
- **Variable:**  
Change from baseline to Week 116 in tau PET median SUVR
- **Treatment:**  
Prescribed study drug including up-titration to the target dose
- **Population-level summary:**  
Difference in variable means between treatment arms
- Intercurrent events

- Substantial reduction in drug exposure due to the COVID-19 pandemic (defined as  $\geq 4$  missed dose-months)
- Treatment discontinuation due to any reason

Tau PET is listed in the protocol under “Pharmacodynamic Biomarker Objective”. Considering that tau PET aims at estimating the Pharmacodynamic effect of treatment, reporting treatment effect estimated "as if there were no treatment discontinuations and no substantial reduction in exposure due to COVID-19 pandemic" (thus using an hypothetical strategy) addresses the scientific question of interest.

Since there are not individual Tau PET substudies for GRADUATE I and GRADUATE II, but rather a single Tau PET substudy across all patients from GRADUATE I and GRADUATE II, Tau PET will be analyzed at the pooled level of GRADUATE I and GRADUATE II.

### **5.7.6.3 Main Analytical Approach**

An MMRM analysis will be used to estimate the mean change from baseline to Week 116 for each of the median SUVRs defined. The model will include the change from baseline in median SUVR as the dependent variable, while adjusting for treatment arm (as categorical), visit (as categorical), APOE  $\epsilon 4$  status (as categorical; carrier vs non-carrier), baseline median SUVR, baseline median SUVR-by-visit, study, study-by-visit and treatment-by-visit interaction. Visit will be treated as the repeated variable within a participant. An unstructured variance-covariance matrix will be applied to model the within-participant errors; in the case of non-convergence, compound symmetry will be used, together with a robust estimator of standard error (“sandwich” estimator).

In line with the estimand definition, data acquired after the ICE “Substantial reduction in drug exposure due to the COVID-19 pandemic” (as defined in [Table 3](#)) or more than 56 days from last dose will be excluded from the analysis and treated as missing for the primary analysis purposes.

There will be no data imputation for missing data. However, the MMRM provides unbiased estimates and valid inference in the presence of missing data, under the MAR (missing at random) assumption. A subgroup analysis by parent study may be also considered in order to derive a study-specific treatment effect.

Based the same MMRM model already described in this section, the change from baseline to week 52 in tau PET will also be reported as supplementary analysis.

### **5.7.6.4 Visit Windowing**

For tau PET assessments, due to the long time between scheduled assessments, time windows based on study days, as defined in [Table 9](#), will be used. Study days are

defined based on days on study since the date of the first dose, with the day of the first dose being Study Day 1.

**Table 9 Time Windows for tau PET Assessments**

Visit	Target study day	Time window
Baseline	1	Up to day 35
Week 52	365	281, 449
Week 116	813	645, 897

### **5.7.7 Cerebrospinal Fluid (CSF) Analyses**

The main analysis for the CSF biomarkers will be based on the pooled dataset of GRADUATE I and GRADUATE II studies (due to the small number of CSF samples within each study). Analyses at individual study level will be conducted as well.

Analysis of CSF biomarkers will be based on the CSF-mITT analysis set unless otherwise specified.

CSF biomarker data will be summarized by treatment group and visit (see schedule of assessment in the study protocol).

*For each CSF biomarker, two statistically equivalent ANCOVA models will be considered:*

- 1. using the change from baseline to Week 116 as dependent variable, with covariates: treatment arm (as categorical), APOE ε4 status (as categorical; carrier vs non-carrier) and baseline biomarker.*
- 2. using the value at Week 116 as the dependent variable, with covariates: treatment arm (as categorical), APOE ε4 status (as categorical; carrier vs non-carrier) and baseline biomarker.*

Both models will use log (base 10) transformed biomarker data. The following summary statistics will be estimated after the appropriate back-transformation of the original model parameters:

- The geometric mean at Week 116 for each treatment arm, obtained as  $10^{\text{LSM}}$ , where LSM is the least square mean for the corresponding treatment arm based on model 2.
- The geometric mean ratio (gantenerumab relative to placebo) at week 116, obtained as  $10^{\text{LSM\_GvsP}}$ , where LSM\_GvsP is the least square means of the contrast of Gantenerumab against placebo based on model 2.
- The %-difference in geometric mean (relative to placebo) at week 116, obtained as  $[(10^{\text{LSM\_GvsP}}) - 1] * 100$  based on model 2.

- *The %-change from Baseline to Week 116 in the Geometric Mean for each treatment arm, obtained as  $[10^{LSM} - 1] * 100$ , where LSM is the least square mean for the corresponding treatment arm at the corresponding visit based on model 1*

There will be no data imputation for missing data.

The following CSF biomarkers will be analyzed:

- Total tau (tTau)
- Phosphorylated tau (pTau-181)
- Neurogranin
- Neurofilament light (NFL)

Other exploratory CSF biomarker may be reported separately.

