Appendix 1: Schedule of Activities (cont.)

Table 2: Week 36 to the End of Study: 510 mg Q2W (cont.)

Assessment/Procedure	Treatment Period											Only for Participants Who Have Completed Week 104 when the 12 week study extension is Implemented		Early Term Visit ^a	Unsched Visit
	Final Efficacy and Safety Assessments											Follow-Up Period for Participants Not Enrolling in the OLE			
	Wk 36	Wk 38	Wk 40	Wk 41	Wk 42–50	Wk 52	Wk 54–74	Wk 76	Wk 78–102	Wk 103	Wk 104 ^{a, b}	Wk 116	Wk 152		
Dose number	10	11	12		13–17 ^c	18 ^a	19–29 ^c	30 ^a	31–43 ^c						
Dose level in milligrams (mg)	510	510	510		510	510	510	510	510						
MRI scan ⁱ	B				Wk 48 ^j		Wk 60	B			x ^j			x ^j	x
CSF ^k and matching serum sampling (for participants enrolled based on CSF eligibility criteria only)								x			x			x ^k	
CDR						P&S P		P&S P			P&SP		P&SP	P&SP	P&SP
ADAS-Cog13						P		P			P		P	P	P
Verbal Fluency Task						P		P			P		P	P	P
Coding						P		P			P		P	P	P
ADCS-ADL						SP		SP			SP		SP	SP	SP
FAQ						SP		SP			SP		SP	SP	SP
MMSE						P		P			P		P	P	P
EQ-5D						SP		SP			SP			SP	SP
QoL-AD						P&S P		P&S P			P&SP			P&SP	P&SP
ZCI-AD						SP		SP			SP			SP	SP
RUD-Lite						SP		SP			SP			SP	SP

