Appendix 1: Schedule of Activities (cont.)

Table 2: Week 36 to the End of Study: 510 mg Q2W (cont.)

- ^k Lumbar puncture must be performed in the morning (between 8:00 a.m. and noon) to minimize potential diurnal variation of CSF parameters and should be performed prior to dosing. For participants enrolling based on CSF eligibility criteria, CSF and matching serum samples are optional at Week 76. Lumbar puncture does not have to be performed the same day as the main Week 76 visit or Week 104 visit, but should be performed in a reasonable time around these visits. The need for CSF collection at early termination visit will be discussed on a case-by-case *based on the participant's condition and the time since last lumbar puncture and advice by the Medical Monitor may be sought*.
- ^l Vital signs include measurements of pulse rate and systolic and diastolic blood pressure. Blood pressure and pulse rate should be taken when the participant is at rest and should not be measured unless at least 15 minutes have elapsed since the last blood draw. The same arm should be used for all blood pressure measurements. Pulse rate will be determined and will be recorded as beats per minute. If obtained manually, the pulse rate should be counted for a minimum of 20 seconds at each assessment.
- ^m Females of childbearing potential (including those who have had a tubal ligation) must have a urine pregnancy test performed at the site prior to each dose administration. If a urine pregnancy test is positive, it must be confirmed by a serum pregnancy test at the central laboratory. Results are to be recorded only in the source documents.
- ⁿ Study drug administration should be performed only after all assessments and rating scales for the participant are completed (unless indicated otherwise). Study drug will be administered to participants by subcutaneous injection (full details are provided in the pharmacy manual). Participants should be observed for up to 2 hours after dosing. After the fourth injection visit, this observation time may be reduced to 1 hour. Study personnel preparing and administering study drug must not be involved with any efficacy assessments or safety evaluations.
- ^o A plasma biomarker sample will be obtained as soon as is practical (e.g., at an unscheduled visit) once the site becomes aware of the occurrence or worsening of ARIA-E or of the occurrence of ARIA-H meeting discontinuation criteria.

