## Visit Windowing

For CSF assessments time windows based on study days, as defined in [Table 10](#), will be used. Study days are defined based on days on study since the date of the first dose, with the day of the first dose being Study Day 1.

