**Table 10 Time Windows for CSF Assessments**

Visit	Target study day	Time window
Baseline	1	Up to day 35
Week 116	813	645, 897

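### SAP Table 10 has no window for the protocol's optional Week 76 CSF sample, so those values enter neither the by-visit summary nor the Week 116 model

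*SAP*

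**What the plan says.** **Protocol.** Appendix 1, Table 2 marks CSF and "matching serum sampling (for participants enrolled based on CSF eligibility criteria only") at Week 76, at Week 104 for those who finished before the extension, and at early termination. Table 3 moves the final sample to Week 116 for everyone else and refers back to Tables 1 and 2 for visits up to Week 103. The footnote on lumbar puncture says that "CSF and matching serum samples are optional at Week 76". It adds that the puncture need not fall on the visit day "but should be performed in a reasonable time around these visits". No number of days is given.

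**SAP.** Section 5.7.7 promises that "CSF biomarker data will be summarized by treatment group and visit (see schedule of assessment in the study protocol"). Under Visit Windowing it then sets the rule: "For CSF assessments time windows based on study days, as defined in" Table 10. That table ("Time Windows for CSF Assessments") has two rows: Baseline, up to Day 35, and Week 116, target Day 813, Days 645 to 897.

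Two ANCOVA models follow, one "using the change from baseline to Week 116 as dependent variable" and the other using the Week 116 value itself. Missing CSF data are not imputed. The two trials are pooled for the main CSF analysis, "due to the small number of CSF samples within each study".

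**The concern.** Section 5.7.7 is at odds with itself. One sentence commits to summarising CSF at the visits in the protocol schedule. The windowing table leaves one of those visits with nowhere to go. Nothing in the section says that Week 76 CSF is excluded, or why.

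Two things are at stake:

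- **Time course.** Week 76 is the only scheduled mid-treatment CSF sample. With one post-baseline window, the four analysed markers cannot be described over time. SAP Table 1 also lists an exploratory endpoint on change over time in plasma and other CSF markers.
- **Participants without a Week 116 sample.** The CSF-mITT set in SAP Table 2 admits anyone with at least one valid CSF value. Someone with baseline and Week 76 CSF but nothing in Days 645 to 897 is in that set, yet contributes nothing to the treatment comparison. The Week 116 result then rests only on those who supplied a late sample.

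**Working it through.** **Inputs.** SAP Table 10: Baseline up to Day 35; Week 116 target Day 813, window 645 to 897. SAP Table 4 (clinical scales): Week 76 target Day 533, window 449 to 630; Week 104 target Day 729. Day 1 is the day of first dose.

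**Reproducing the plan's own days.** Study day = 7 × week + 1.

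- Week 116: 7 × 116 + 1 = 813, as in Table 10.
- Week 104: 7 × 104 + 1 = 729, as in Table 4.
- Lower limit: 729 − 84 = 645. Upper limit: 813 + 84 = 897. The single post-baseline window therefore runs from 12 weeks before Week 104 to 12 weeks after Week 116.

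**Placing Week 76.** 7 × 76 + 1 = 533, as in Table 4.

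- After the baseline window closes: 533 − 35 = 498 days.
- Before the Week 116 window opens: 645 − 533 = 112 days, or 16 weeks.
- Day 533 is in neither window.

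**Allowing for a flexible puncture date.** The protocol gives no tolerance for CSF. As an assumption, take the 3-day dosing-visit window plus the 4 weeks allowed for late cognitive assessments, 31 days in all. The sample then falls on Days 502 to 564, still in no window. Only a puncture at least 112 days late would be used, and it would be labelled Week 116.

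**Comparing with plasma.** Plasma is scheduled at Weeks 24, 52, 104 and 116 after screening. SAP Table 11 has a window for each of these, and 5.7.8 fits a repeated-measures model across them.

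**Checking that a Week 76 row fits.** With the Table 4 limits, Days 449 to 630, the row ends 645 − 630 = 15 days before the Week 116 window opens. There is no overlap. Days 36 to 448 and 631 to 644 stay unassigned, so early-termination CSF taken on those days needs its own rule.

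**The case against.** The strongest reply is that the main analysis is coherent as written. The pharmacodynamic endpoint is change from baseline to Week 116, and protocol version 5 revised it to specify that period. The CSF-longitudinal set also requires a Week 116 value. A single-visit ANCOVA fits this, and a new window alone would not alter it. SAP 5.3.3 itself notes that, with complete data, single-visit ANCOVA and a repeated-measures model with visit-specific coefficients give identical estimates. Week 76 therefore adds little for anyone who also has a Week 116 sample. All of this stands. It confines the gain to participants with Week 76 but no Week 116 CSF, and it does not remove the conflict over the by-visit summary.

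The comparison with plasma is also imperfect. Plasma is drawn from every participant, whereas the Week 76 CSF sample is optional and limited to a subset. The plasma and PET tables leave day ranges unassigned too. But no scheduled plasma visit is left without a window, and here a scheduled CSF visit is.

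Three stronger readings are tempting, and the documents do not support them:

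- **That the SAP admits its CSF analysis is short of samples.** The remark on small numbers concerns each study separately and is the reason for pooling. It says nothing about the pooled analysis.
- **That the long uncovered stretch (Days 36 to 644) measures the data lost.** It counts calendar days. Only one scheduled CSF visit, an optional one, lies in it.
- **That participants had a puncture whose data go unused.** Protocol 4.5.6.2 and 4.5.6.4 also assign CSF to gantenerumab concentration, and 4.5.6.2 to exploratory markers. Protocol 6.6 and SAP section 1 place the PK reporting outside this analysis. Only the Week 76 values of the four listed markers lack a place.

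**Conclusion.** The point holds as a gap between the promised by-visit summary and the windows meant to deliver it. Timely Week 76 values of tTau, pTau-181, neurogranin and NFL are assigned to no visit, so they enter neither the summary nor the Week 116 model.

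The conclusion rests on one inference. The SAP does not say outright that out-of-window CSF is discarded; this follows from its rule that Table 10 is used and from the absence of imputation.

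The effect on the Week 116 contrast cannot be computed, because no document gives the number of Week 76 samples or of participants with Week 76 but no Week 116 CSF. It could be negligible. A repeated-measures model would let those participants contribute under a missing-at-random assumption, which the SAP already accepts for plasma. The primary endpoint and the confirmatory secondary endpoints are untouched. The change is worth making because it is cheap and uses a model already in the SAP.

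**What to change.** 1. Add a Week 76 row to Table 10: target Day 533, Days 449 to 630 as in Table 4. Report Week 76 as supplementary.
2. Estimate the Week 116 contrast with the 5.7.8 plasma model on the log10 scale: treatment, visit, treatment-by-visit, APOE ε4 status, baseline and baseline-by-visit. Keep Week 116 as the endpoint and the Week 116 ANCOVA as a supportive analysis.
3. State how early-termination CSF is assigned to a visit, with a limit on time since last dose, such as the 56 days the SAP uses for PET. Say what happens to samples that still fall in no window.
4. Settle these rules before unblinding, so that any use of Week 76 CSF is not post hoc.

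**Cost.** SAP wording and a small programming change that reuses the plasma code. No new data are needed. The model is slightly larger and may be less stable if Week 76 samples are few. The fallback already in 5.7.8, compound symmetry with sandwich standard errors, covers non-convergence.
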